4.2 Trial endpoints

Primary Objective:	Primary Endpoint:
To explore the clinical efficacy of MC2-25 cream compared to MC2-25 vehicle in adults with CKD-aP	 Mean change in weekly mean Worst Itch Numeric Rating Score (WI-NRS) recorded in the subject's diary from Baseline to Week 12 for MC2-25 cream compared to MC2-25 vehicle. (Weekly mean WI-NRS is calculated as the average of WI-NRS values recorded in the subject's diary 7 days prior to and including the visits.)
	Secondary Endpoints:
	 Percentage of subjects obtaining a ≥4-point improvement in weekly mean WI-NRS recorded in the subject's diary from Baseline to Week 12 for MC2-25 cream compared to MC2-25 vehicle.
	• Percentage of subjects obtaining a ≥3-point improvement in weekly mean WI-NRS recorded in the subject's diary from Baseline to Week 12 for MC2-25 cream compared to MC2-25 vehicle.
	 Percentage of subjects obtaining a complete response in weekly mean WI-NRS recorded in the subject's diary from Baseline to Week 12 for MC2-25 cream compared to MC2-25 vehicle. (Complete response is defined as scores equal to 0 or 1 in ≥80% of the non-missing WI-NRS values recorded in the subject's diary 7 days prior to and including the visits.)
	Other Endpoints:
	• Mean change in WI-NRS recorded during on-site visits from Baseline to Week 12 for MC2-25 cream compared to MC2-25 vehicle.
	• Mean change in Sleeploss due to Itch Numeric Rating Score (SI-NRS) from Baseline to Week 12 for MC2-25 cream compared to MC2-25 vehicle.
	• Mean change in Skin Dryness Numeric Rating Score (SD-NRS) from Baseline to Week 12 for MC2-25 cream compared to MC2-25 vehicle.

	 Percentage of subjects who reported "Much better" or "A little better" in Subject's Global Impression of Change (SGIC) for Worst Itch (WI), Sleeploss due to Itch (SI), or Skin Dryness (SD) from Baseline to Week 12 for MC2-25 cream compared to MC2-25 vehicle.
	• Percentage of subjects who reported an important improvement in SGIC for WI, SI, or SD at Week 12 for MC2-25 cream compared to MC2-25 vehicle.
	• Change in treatment area size from Baseline to Week 12 for MC2-25 cream compared to MC2-25 vehicle.
	• Change in 5D-Itch from Baseline to Week 12 for MC2-25 cream compared to MC2-25 vehicle.
	• Change in Skindex-10 from Baseline to Week 12 for MC2-25 cream compared to MC2-25 vehicle.
	• Change in EQ-5D-5L from Baseline to Week 12 for MC2-25 cream compared to MC2-25 vehicle.

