6.3 Dosing regimen

MC2-25 cream or MC2-25 vehicle is to be applied twice daily, in the morning and evening, to areas with CKD-aP. The treatment must be applied in a thin even layer to affected areas and rubbed in gently to ensure that the treatment areas are saturated. Treatment of all areas with CKD-aP must be continued until the Week 12 (or EoT) visit. This is also applicable for areas becoming itch-free during trial participation and new areas of CKD-aP identified after the Baseline visit.

The daily dose should not exceed 50 g. Detailed application instructions will be provided in the subject instructions.

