Diary (Handout)	Х	Х	Х		Х		Х			
Biopsy ¹⁵		Х							Х	
Tape stripping ¹⁶		Х							Х	
Prior & concomitant therapies ¹⁷	Х	Х	Х	Х	Х	Х	Х	Х	Х	Х
Adverse events		Х	Х	Х	Х	Х	Х	Х	Х	Х
Investigational medicinal product (IMP) dispensation		Х			Х		Х			
IMP return, compliance and accountability					Х		Х		Х	
IMP application ¹⁸				_	Х					
Diary (Review)		Х	Х		Х		Х		X	

- 1. Follow-up (FU) visit is only applicable if there are ongoing serious adverse events (SAEs) or related adverse events (AEs) at Week 12. (X) indicates assessments to be performed if judged necessary by the investigator.
- 2. An unscheduled visit can be conducted to perform any of the postbaseline assessments or procedures included in the SoA if deemed necessary by the Investigator.
- 3. In the case of trial withdrawal or treatment discontinuation, all assessments of the Week 12 (End of Treatment [EoT]) visit have to be performed. The end of treatment form must be completed when treatment is discontinued and the end of trial form must be completed at end of the trial or in case of trial withdrawal.
- 4. Phone calls: To remind subjects about diary documentation (in particular once-daily WI-NRS assessments that must be performed for 8 days leading up to each on-site visit [i.e., from day -7 to day 0 where day 0 = next on-site visit day]) and to ask for AEs. Phone visits may be replaced by in-clinic visits where relevant, e.g., in subjects going to the dialysis unit for haemodialysis.
- 5. Informed consent must be signed by both subject and investigator before any trial-related procedures are performed.

Clinical Trial Protocol

Protocol No. MC2-25-C1 Vers.3.0 EU/30-Nov-2022

- 6. At-home (diary) assessments must be performed for 8 days leading up to each visit, i.e., from day -7 to day 0 where day 0 = next on-site visit day.
- 7. The WI-NRS must also be reported by the subject at on-site visits
- 8. At all on-site visits, all patient-reported outcome (PRO) assessments should be completed before all other clinical assessments or procedures.
- 9. The trial staff must estimate the % body surface area treated based on the subject's indication of CKD-aP treatment area size on the CKD-aP treatment area diagram.
- 10. Physical exam: A complete physical examination is required at Screening and Week 12 (EoT or Early Termination) visits. An abbreviated physical examination is required at the Baseline visit (and if judged necessary by the investigator) at the FU visit if the FU visit is applicable.

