7.9.7 Subject's indication of CKD-aP treatment area size

The subject must indicate the size of the CKD-aP treatment area (by greying out all areas treated) at Baseline, Week 1, Week 4, Week 8, and Week 12 or Early Termination using the CKD-aP treatment area diagram below, if necessary, with assistance from trial staff. Subsequently, trial staff must estimate the size of the treatment area (in terms of % body surface area treated) based on the CKD-aP treatment area diagram:

CKD-aP treatment area diagram – according to subject (example)

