3.4 Other Efficacy Endpoints

Other endpoints compare MC2-25 cream and MC2-25 vehicle and are:

- Mean change in WI-NRS recorded in the subject's diary from Baseline to Week 1, Week 4, and Week 8.
- Mean change in WI-NRS recorded during on-site visits from Baseline to Week 1, Week 4, Week 8 and Week 12.
- Mean change in Sleeploss due to Itch Numeric Rating Score (SI-NRS) from Baseline to Week 1, Week 4, Week 8 and Week 12.
- Mean change in Skin Dryness Numeric Rating Score (SD-NRS) from Baseline to Week 1, Week 4, Week 8 and Week 12.

Table 2WI-NRS, SI-NRS, SD-NRS scale and scores:

Worst Itch/ Worst Sleep Loss/ Worst Skin Dryness in last 24 hours											
0	1	2	3	4	5	6	7	8	9	10	
No Itch/										Worst	
No										Imaginable	
Sleeploss/										Itch/	
No Skin										Sleeploss/	
Dryness										Skin	
-										Dryness	

- Percentage of subjects who reported an improvement in Subject's Global Impression of Change (SGIC) (i.e. "Very much better", "Much better" or "A little better") will be reported for Week 1, Week 4, Week 8 and Week 12 for WI-NRS, SI-NRS and SD-NRS.

Note: SGIC will be summarized for all subjects (see Table 3). Categories 1 to 3 will be summarized as combined "Improvement in SGIC score". Categories 1 to 7 will be summarized individually.

Table 3SGIC for itch, sleep loss and skin dryness.

Choose response that best describes overall change in itch, sleep loss and skin dryness since you started taking the trial medication.

since jou sur ou withing the true incurations							
Improvement in	1	Very much better					
SGIC	2	Much better					
(1 to 3)	3	A little better					
	4	No change					
	5	A little worse					
	6	Much worse					
	7	Very much worse					

- Percentage of subjects who reported "an important improvement" in Subject's rating of importance of improvement (i.e., subjects who respond "Yes" to Question 1 in the 'Subjects rating of importance' assessment) for WI, SI, and SD at Week 1, Week 4, Week 8, and Week 12 or ET.
- Mean change in Subject's indication of CKD-aP treatment area size from Baseline to Week 4, Week 8 and Week 12.
- Mean change in 5D-Itch (Domain Scores and Total Score) from Baseline to Week 4, Week 8 and Week 12

The 5D-Itch consists of 5 domains numbered 1-5.

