- Domains 1-3 are single item (question) domains exploring the Duration (Duration domain), Degree (Degree domain) and Direction (Direction domain) of Itch. For each of domains 1-3 the domain score is equal to the value indicated below the response choice (range 1–5).
- Domain 4 (Disability domain) includes four items (questions) assessing the impact of itching on daily activities: sleep, leisure/social activities, housework/errands and

work/school). For domain 4 the score is achieved by taking the highest score on any of the four items (range 1-5).

- Domain 5 (Distribution domain) assesses the number of affected body parts out of 16 possible options. For domain 5 the score is obtained by tallying the number of affected body parts and the sum is sorted into five scoring bins: sum of 0-2 = score of 1, sum of 3-5 = score of 2, sum of 6-10 = score of 3, sum of 11-13 = score of 4, and sum of 14-16 = score of 5 (range 1-5).
- The total score is achieved by summing together the 5 domain scores and can therefore range between 5 (no pruritus) and 25 (most severe pruritus).
- Continuous descriptive statistics will be provided for all individual domains except Domain 5 from Baseline to Week 4, Week 8 and Week 12.
- Mean change in 5D-Itch Total Score will be presented using continuous descriptive statistics from Baseline to Week 4, Week 8 and Week 12.

1. Duration	During the last 2 weeks, how many hours a day have you bee itching?						
	Less than 6hrs a day	6-12hrs/ day	12-18hrs/ day	18-23hrs/ day	All day		
	1	2	3	4	5		
2. Degree	Please rate	the intensity of	of your itching	g over the pa	st 2 weeks		
	Not	Mild	Moderate	Severe	Unbearabl		
	Present				e		
	1	2	3	4	5		
3. Direction	Over the p	ast 2 weeks l	has your itch	ing got bette	er or worse		
	compared t	o the previous	s month?				
	Completel	Much	Little bit	Unchanged	Getting		
	y resolved	better, but	better, but		worse		
		still present	still present				
	1	2	3	4	5		
4. Disability	Rate the im	pact of your i	tching on the	following act	tivities over		
	the last 2 w	eeks		1			
• Sleep	Never	Occasionall	Frequently	Delays	Delays		
	affects	y delays	delays	falling	falling		
	sleep	falling	falling	asleep and	asleep and		
		asleep	asleep	occasionall	frequently		
				y wakes me	wakes me		
				up at night	up at night		
	1	2	3	4	5		
• Leisure/	Never	Rarely	Occasionall	Frequently	Always		
social	affects this	affects this	y affects	affects this	affects this		
• Housewor	activity	activity	this activity	activity	activity		

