- 1. Weight of IMP used during the trial per subject
- 2. Weight of IMP used during the trial per subject per number of weeks on treatment
- 3. Weight of IMP used during the trial per subject per % BSA at Baseline
- 4. Weight of IMP used during the trial per subject per number of weeks on treatment per % BSA at Baseline

Weight of IMP used during the trial per subject = $(74.8 \text{ grams times the total number of tubes returned at Week 4, Week 8, and Week 12 visits) + (50 grams times the total number of dispensed tubes not returned) – (the sum of the weight of all tubes returned at Week 4, Week 8, and Week 12 visits). Notes: The minimum weight of IMP used is 0 grams. Number of weeks on treatment is defined as the period from first to last application expressed in weeks.$

Drug accountability information will be summarized for SAS and listed by subject.

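### Under the dosing rule the treated area cannot shrink, so its change cannot show that itch has cleared, and the SAP leaves the other measure of itch extent out of its domain statistics

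*Protocol*

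**What the plan says.** Protocol 6.3 sets how long each area is treated: "Treatment of all areas with CKD-aP must be continued until the Week 12 (or EoT) visit". It continues: "This is also applicable for areas becoming itch-free during trial participation and new areas of CKD-aP identified after the Baseline visit".

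Protocol 7.9.7 sets what is recorded at Baseline and Weeks 1, 4, 8 and 12: "The subject must indicate the size of the CKD-aP treatment area (by greying out all areas treated". A footnote to the visit schedule (Protocol 7.1, Table 3) turns the drawing into a number: "The trial staff must estimate the % body surface area treated based on the subject's indication of CKD-aP treatment area size".

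Protocol 4.2 places the result under the primary (efficacy) objective, among the other endpoints: "Change in treatment area size from Baseline to Week 12 for MC2-25 cream compared to MC2-25 vehicle". SAP 3.4 keeps it as an other efficacy endpoint: "Mean change in Subject's indication of CKD-aP treatment area size from Baseline to Week 4, Week 8 and Week 12". Neither document separates treated skin that still itches from treated skin that has cleared, and neither states which direction counts as benefit.

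The other planned measure of how widespread the itch is comes from Domain 5 of the 5D-Itch, a count of affected body parts out of 16 sorted into five bins. The SAP 3.4 endpoint line covers the domain scores as well as the total. The detail below it then says: "Continuous descriptive statistics will be provided for all individual domains except Domain 5". The list of changes from the protocol in SAP 6.2 does not mention this exception.

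SAP 5.6.2 also uses treated area as a denominator for exposure: "Weight of IMP used during the trial per subject per % BSA at Baseline".

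**The concern.** An efficacy endpoint on area invites the reader to take a decrease as improvement. Here the recorded quantity follows the dosing instruction, and that instruction does not let a cleared area leave the count. A subject whose itch has gone from half the affected skin and a subject with no clearance at all record the same change if both adhere and neither develops new areas.

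At stake is the reading of one descriptive table. A null or positive mean change could be taken as lack of effect on extent, and a negative one as benefit, when neither follows. Domain 5 could answer the question of extent from data already collected, but the SAP's statement of which domains to summarise passes over it.

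**Working it through.** The plan gives no figure to reproduce on this point. The check is one of logic, with assumed numbers to show size.

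**Step 1, the identity.** Let A0 be the area treated at Baseline, N(t) the new areas added by visit t, and C(t) the area cleared by visit t. Under Protocol 6.3, with adherence:

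- treated area: A(t) = A0 + N(t), so change = N(t) ≥ 0
- itching area: I(t) = A0 − C(t) + N(t), so change = N(t) − C(t)

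Clearance, C(t), does not appear in the change in treated area.

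**Step 2, one subject (assumed).** Baseline 20% BSA, half of it clears, one new area of 5%. Treated: 20 + 5 = 25, change +5. Itching: 20 − 10 + 5 = 15, change −5. The two quantities move in opposite directions.

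**Step 3, group means (assumed).** Baseline extent is spread evenly from 5% to 50% BSA, so the mean is 27.5 and the mean unaffected skin is 100 − 27.5 = 72.5. New itch on 2% of unaffected skin is 0.02 × 72.5 = 1.45. Clearance of 80% is 0.8 × 27.5 = 22.0, and of 30% is 0.3 × 27.5 = 8.25.

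| Scenario | Change in itching area | Change in treated area |
|---|---|---|
| 80% cleared, 2% new | 1.45 − 22.0 = −20.55 | +1.45 |
| 30% cleared, 2% new | 1.45 − 8.25 = −6.80 | +1.45 |
| 80% cleared, none new | −22.0 | 0 |
| 80% cleared, 2% new, a quarter of cleared skin no longer treated | −20.55 | 1.45 − 0.25 × 22.0 = −4.05 |

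The first two rows differ by 13.75 points in itching area and by nothing in treated area. A negative mean appears only in the last row, where the dosing rule is not followed.

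**Step 4, what the contrast can still show.** If one arm has new itch on 2% of unaffected skin and the other on 5% (0.05 × 72.5 = 3.63), the treated-area changes are +1.45 and +3.63, a difference of about 2.2 points. Less spread is visible; clearance is not.

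**Step 5, Domain 5.** Each domain scores 1 to 5 and the total runs from 5 to 25. Domain 5 can therefore account for at most 4 of the 20 points of range, or 20%, so the total is a weak substitute for it. The bins are also coarse: a fall from 10 to 6 affected body parts stays at score 3, while a fall from 11 to 10 moves from 4 to 3. This is why the raw count should be shown beside the score.

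**Step 6, the exposure denominator (assumed growth).** Suppose 15% BSA is treated at Weeks 0 and 1, and 20% at Weeks 4, 8 and 12. The time-weighted (trapezoidal) mean is (1 × 15 + 3 × 17.5 + 8 × 20) / 12 = 227.5 / 12 = 18.96. Grams per Baseline % BSA would then be 18.96 / 15 = 1.26 times grams per % BSA actually treated. A plain average of the five readings is 18.0, because two of the five fall in the first week, so time weighting is preferable. With no growth the ratio is 1. The documents give no growth figure.

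**The case against.** Four stronger readings are tempting, and the other side is right to resist each.

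- **That the endpoint can never show benefit.** A reader might infer this, but Protocol 4.2 defines a comparison between arms. Since new areas are added, slower spread on cream would show as a smaller increase. What stands is that shrinkage of the itching area cannot be seen.
- **That any recorded decrease proves non-compliance.** The subject redraws the diagram at each visit and staff estimate % BSA from it. Drawing and estimation error can produce decreases in fully adherent subjects. The non-negative result applies to the true treated area, not to every recorded value. The documents also give no basis for supposing that cream subjects would stop treating cleared skin more often.
- **That Domain 5 is lost.** It still enters the 5D-Itch total and, under SAP 5.5.3, the subject listings. SAP 5.5.3 also promises descriptive summaries of all other efficacy endpoints, and SAP 5.1 provides frequencies for categorical variables, so a frequency table could be argued for. SAP 3.4 does not say so: it includes domain scores in the endpoint line and then excepts Domain 5 without naming a replacement.
- **That the exposure figure is biased.** It is labelled as per Baseline % BSA and reports exactly that, beside two averages with no area denominator. Any gap from grams per % BSA actually treated rests on assumed growth.

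It is also fair to say that Protocol 6.8 already collects treatment area size together with the question on use as prescribed, so part of the remedy is relabelling. That supports the remedy, because the protocol itself treats the measure as one of compliance.

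**Conclusion.** The point holds as a minor one. In adherent subjects the true treated area is the Baseline area plus new areas, so its change carries no information on clearance. Read as efficacy, it can at most show a difference in spread. This follows from the text of Protocol 6.3 and 7.9.7 alone; only the sizes in the illustration rest on assumed clearance, new-area and adherence rates.

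The Domain 5 exception conflicts with the SAP's own endpoint line and is unexplained. It removes from the stated domain statistics the one collected item that could show itch becoming less widespread, subject to its limits: it counts body parts, not area, and looks back over two weeks.

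Both endpoints are descriptive. The primary WI-NRS analysis, the responder analyses and the sample size do not depend on them.

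**What to change.** Three changes to the SAP, the third optional, all using data already collected:

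1. In SAP 3.4, report treated % BSA by visit and arm as exposure and compliance, in line with Protocol 6.8. State that its change is not interpreted as improvement in itch, and record the departure from Protocol 4.2 in SAP 6.2.
2. In SAP 3.4, remove the exception for Domain 5. Summarise it by visit and arm as the measure of itch extent: score frequencies, change in score, and the raw count from 0 to 16.
3. Optional, in SAP 5.6.2: add grams per time-weighted mean treated % BSA beside the existing per-Baseline figure, without replacing it.

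The cost is a few lines of SAP text and one or two more descriptive tables. The dosing and endpoint passages need to be reconciled, and this does so without touching the dosing rule.

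Having subjects also mark the areas that currently itch would give a direct area measure. It is not part of this fix: it changes data collection, would need an amendment under Protocol 9.1, and could not recover visits already completed.

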6.4 Dose modification

Not applicable.

6.5 Packaging, labelling and storage

MC2-25 cream and MC2-25 vehicle are identical in appearance and packaging.

Medication labels for the IMPs will comply with the legal requirements of the country where the trial is performed and be printed in the local language.

The IMPs will be supplied by MC2's designated vendor and will be stored securely at the site under the control of the investigator. The temperature will be monitored and documented.

The IMP will be supplied to the clinical site(s) as tubes containing 60 g of product. The IMP is to be stored at a temperature of 2° to 8°C at the site, and below 25°C after dispensing to the subject. At all times, the IMP tube should be protected from direct sunlight exposure.

6.6 Assignment to treatment

6.6.1 Randomisation

Randomisation will be performed using a validated system that automates the random assignment of treatment groups to randomisation numbers. Treatment assignment will be via a central interactive web response (IWR) system in accordance with a pre-planned computer-generated randomisation schedule in a 2:1 ratio.

Randomisation will be stratified according to the following CKD stage strata:

A. ≥40% of subjects must be on dialysis (HD or HDF) and must be CKD stages 4-5

- B. $\geq 20\%$ of subjects must Not be on dialysis and must be CKD stages 4-5
- C. $\geq 20\%$ of subjects must Not be on dialysis and must be CKD stage 3

Randomisation data will be kept strictly confidential, accessible only to authorised persons, until the time of unblinding.

A subject who fulfils the trial eligibility requirements will be randomly assigned to treatment.

6.6.2 Blinding

This is a double-blind trial. The sponsor, sponsor representatives, and all subjects, monitors, and trial personnel will be blinded throughout the trial. Instructions for emergency unblinding are provided in Section 13.1.

6.7 **Prior, concomitant, and prohibited therapies**

Medications and therapies are hereafter referred to as therapies. All therapies (i.e., prescription drugs [including COVID-19 vaccination programs, see Table 1], dialysis treatment regimen, over-the-counter [OTC] drugs and vitamins, herbal and dietary supplements) taken within 30 days prior to screening will be recorded as prior therapies at the Screening visit.

Thereafter, all therapies used during the course of the trial will be recorded as concomitant therapies. Information regarding the total daily dose, route of administration, start and discontinuation dates, and indication are to be recorded on the subject's eCRF.

6.7.1 **Prohibited therapies prior to baseline**

A number of therapies are prohibited during the period leading up to baseline as outlined in Table 2.

Table 2:Prohibited Therapies Prior to Baseline

Prohibited Therapy	Exclusion Criterion	Applicable Period Prior to Baseline (Day 0)
Start of a new or a change to existing systemic treatment for CKD-aP, including but not limited to antihistamines, corticosteroids, opioids, GABA analogues, or kappa opioid receptor agonists (Section 5.3).	13	21 days
Use of emollients on CKD-aP areas within 10 days prior to the Baseline visit	14	10 days
Use of any topical treatment on CKD-aP areas, including but not limited to antihistamines, or corticosteroids. Note: standard topical treatments used on or around a haemodialysis access site are allowed, e.g., local anaesthetics, sterilants.	15	21 days
Use of any light therapy for CKD-aP, including but not limited to UV-B	16	35 days
Start of new or change of existing non-biologic systemic immunosuppressive treatment, including but not limited to corticosteroids, cyclosporin, and tacrolimus.	17	5 weeks
Start of new or change of existing biologic systemic treatment, including but not limited to etanercept, adalimumab, alefacept, infliximab, and ustekinumab	18	3 months or 5 half-lives (whichever is longer)

Therapies not listed are allowed.

